2 STUDY OBJECTIVES AND ENDPOINTS

2.1 Primary Objectives

The primary objectives of this study are:

- To investigate the safety and tolerability of treatment with oral trofinetide in girls two to five years of age who have Rett syndrome
- To characterize the pharmacokinetics of oral trofinetide in girls two to five years of age who have Rett syndrome

Final Version: 1.0 Date: 19 December 2022

2.1.1 Primary Endpoints

The safety endpoints are as follows:

- treatment-emergent adverse events (TEAEs)
- serious adverse events (SAEs)
- withdrawals due to adverse events (AEs)
- potentially clinically important changes in other safety assessments

The pharmacokinetic (PK) endpoints are as follows:

- whole blood concentration of trofinetide
- trofinetide PK parameters using the population PK approach

2.2 Exploratory Efficacy Objectives

The exploratory efficacy objectives of this study are:

- To investigate the efficacy of treatment with oral trofinetide in girls two to five years of age who have Rett syndrome
- To investigate the benefit of treatment with oral trofinetide on overall quality of life for girls two to five years of age who have Rett syndrome

2.2.1 Exploratory Efficacy Endpoints

The exploratory efficacy endpoints for this study are:

- Clinical Global Impression–Improvement (CGI-I) score at Weeks 2, 4, 8, 12, 24, 52, 78, and end of treatment (EOT)
- Change from Baseline to Weeks 2, 4, 8, 12, 24, 52, 78, and EOT in Clinical Global Impression–Severity (CGI-S) score
- Caregiver Global Impression–Improvement (CaGI-I) score at Weeks 12, 24, 52, 78, and EOT
- Change from Baseline to Weeks 12, 24, 52, 78, and EOT in Overall Quality of Life Rating of the Impact of Childhood Neurologic Disability (ICND) Scale

3 STUDY DESCRIPTION

3.1 Overview of Study Design

This is a multicenter, open-label study of trofinetide for the treatment of girls 2 to 5 years of age with RTT. Participating girls 2 to 4 years of age must weigh \geq 9 kg and \leq 20 kg. Girls 5 years of age who weigh \geq 9 kg and \leq 12 kg can also be enrolled.

Study: ACP-2566-009 Clinical Study Protocol Amendment 2

Approximately 10 to 15 subjects are expected to be enrolled, at least 1 subject who weighs ≥9 to <11 kg, and at least 4 subjects who are less than 4 years of age at Screening, including at least one subject who is 2 years of age. Approximately 10 sites will participate in this study.

The duration of the study will be 26 months and will have three main periods (Figure S-1):

- Screening period: up to 4 weeks
- Treatment period

o Period A: 12 weeks

o Period B: up to approximately 21 months

• Safety follow-up period: 30 days

The schedule of events and assessments is provided in Table S–1 (Screening, Baseline, and Treatment Period A) and Table S–2 (Treatment Period B, and Safety Follow-Up).

Study drug will be dispensed at the site during the Baseline visit when the visit is conducted in the clinic. For the remainder of the study, investigational product will be shipped directly to the subject. Study drug shipment, return, and accountability will be performed in accordance with the drug distribution plan.

The study start date is defined as the date the first subject is enrolled, which is the baseline visit date for the first subject.

The primary completion date is the last date that subject data was collected for the primary outcome measure.

The study completion date is defined as the last date that subject data was collected for the primary outcome measure, secondary outcome measure(s), and adverse events, which includes the safety follow-up telephone call visit.

Procedures for when a subject is lost to follow-up are provided in Section 4.5.

The Sponsor may discontinue the study for any reason.

3.1.1 Screening Period (Up to 4 Weeks)

During the Screening period, subjects will be assessed for study eligibility and prohibited medications will be discontinued if medically appropriate. Subject eligibility will be assessed by the site and the Sponsor through an eligibility review process. Only those subjects who meet all inclusion and no exclusion criteria will be eligible for the study.

Subjects will be evaluated for the diagnosis of RTT. In addition, there must be verified documentation of a *MECP2* mutation.

Final Version: 1.0

Study: ACP-2566-009

Final Version: 1.0 Date: 19 December 2022 Clinical Study Protocol Amendment 2

Investigators should not withdraw a subject's prohibited medication for the purpose of enrolling them into the study. Medications should be discontinued only if it is deemed clinically appropriate to do so and in consultation with the treating physician. The investigator should consider decreasing or discontinuing laxatives before the baseline visit to mitigate possible gastrointestinal side effects from trofinetide administration.

Caregivers will begin to keep a semi-structured caregiver diary during the Screening period.

3.1.2 **Treatment Period A (12 Weeks)**

Treatment Period A is designed for evaluation of the dosing, tolerability, and pharmacokinetics of trofinetide in this population. Exploratory efficacy assessments will also be conducted. The duration of Treatment Period A is approximately 12 weeks (Table S-1), the same length as the double-blind, placebo controlled study in girls and women 5 to 20 years of age.

The Baseline and Week 12 visits must be done at the clinic. All other study visits may be done in the clinic or off-site. Study visits may be done off-site at the discretion of the Principal Investigator and only with the prior approval of the Sponsor or Medical Monitor. When a study visit takes place off-site, the physical examination will not be required. Weight should be measured whenever possible at off-site visits.

The Baseline visit (Visit 2) may occur after screening procedures are completed and have not ruled the subject out of eligibility for the study.

Dosing is twice a day, once in the morning and once in the evening. The study drug must not be mixed with any food or liquid, including water. Immediately after administration of the study drug, food or liquid may be consumed if required.

The first dose of study drug will be administered after all Baseline assessments are completed, or, if the Investigator judges that it is too late in the day, on the following day. In that case, the second day is still considered part of the Baseline visit.

The day the first dose is taken will be considered Day 1. A triplicate ECG must be performed 2 hours (±15 minutes) after the first dose. Two PK samples will also be collected after the first dose: the first, 2 hours (± 15 minutes) after dosing, as close as possible to the postdose ECG, and the second, at least 1 hour after the first. Study drug must be discontinued in the event that a post-Baseline QTcF (QT interval corrected using Fridericia's correction method) duration of \geq 500 ms or an increase of \geq 60 ms compared to the average QTcF interval at Baseline (before dosing) is observed.

After Treatment Period A (and the 30-day follow-up period, if applicable) is completed by all participants, an interim clinical study report of those data will be written. A final clinical study report will be written after the entire study is completed.

3.1.3 **Treatment Period B (Up to Approximately 21 Months)**

Treatment Period B is designed to assess the safety and exploratory efficacy of long-term treatment with trofinetide. Treatment Period B is similar in design and objectives to the open-label extension studies in girls and women 5 to 20 years of age.

During Treatment Period B, subjects will have assessments completed at 24 weeks and 52 weeks after the Baseline visit and then every 26 weeks (6 months) thereafter until the study concludes or is terminated. Assessments may be completed in the clinic or off-site. Study visits may be done off-site at the discretion of the Principal Investigator and only with the prior approval of the Sponsor or Medical Monitor.

3.1.4 Safety Follow-Up Period (30[+4] Days)

A 30(+4)-day safety follow-up telephone or telemedicine contact is to be completed for subjects who complete the treatment period of the study or discontinue prematurely from the study (and do not begin to take marketed trofinetide within the 30 days after completing the treatment period of the study). The telephone or telemedicine contact includes assessment of concomitant medications and treatments and assessment of AEs.

The study schematic is provided in Figure S–1.

The schedule of assessments is provided in Table S-1 (Screening, Baseline, and Treatment Period A) and Table S-2 (Treatment Period B, and Safety Follow-Up).

SUBJECT ELIGIBILITY AND WITHDRAWAL CRITERIA

To be eligible for this study, subjects must meet all of the inclusion criteria and none of the exclusion criteria.

4.1 **Inclusion Criteria**

A subject must meet all of the following inclusion criteria to be eligible for participation in the study:

- 1. Informed consent prior to the conduct of any study procedures is required as follows:
 - a. Written informed consent will be obtained from the legally acceptable representative (LAR). The process of obtaining informed consent will be conducted in accordance with institutional review board (IRB) or ethics committee (EC) policy and applicable local law.

b. The subject's caregiver must also provide informed consent regarding their participation in the study prior to participating in any study procedures.

- 2. Female subject
 - a. 2 to 4 years of age and body weight ≥9 kg and <20 kg at Screening OR
 - b. 5 years of age and body weight ≥9 kg and <12 kg at Screening
- 3. Can swallow the study medication provided as a liquid solution or can take it by gastrostomy tube
- 4. The subject's caregiver is English-speaking and has sufficient language skills to complete the caregiver assessments

Diagnosis

- 5. Has classic/typical Rett syndrome (RTT) or possible RTT according to the Rett Syndrome Diagnostic Criteria (Appendix A)
- 6. Has a documented disease-causing mutation in the MECP2 gene
- 7. Has a CGI-S score of ≥4 at Screening and Baseline

Concomitant Treatment

- 8. If the subject is taking or was taking an anticonvulsant or any other CNS-active medication (including cannabinoids):
 - a. the treatment regimen has been stable for at least 4 weeks before Baseline and there is no current plan to change the dose, OR
 - b. if the medication was discontinued, the discontinuation has occurred no fewer than 2 weeks or 5 half-lives (whichever is greater) before Baseline
- 9. If the subject is taking or was taking any other medication daily for chronic illness (not including antibiotics, pain relievers, or laxatives):
 - a. the treatment regimen of the medication has been stable for at least 2 weeks before Baseline and there is no current plan to change the dose, OR
 - b. if the medication was discontinued, the discontinuation has occurred no fewer than 2 weeks or 5 half-lives (whichever is greater) before Baseline
- 10. If the subject is receiving or was receiving a non-pharmacologic somatic treatment (e.g., a ketogenic diet or vagal nerve stimulation):
 - a. the treatment regimen has been stable for at least 2 weeks before Baseline and there is no current plan to change the treatment, OR
 - b. if the treatment was discontinued, the discontinuation has occurred no fewer than 2 weeks before Baseline

Seizures

11. Has a stable pattern of seizures, or has had no seizures, within 8 weeks prior to Screening

Place of Residence

12. Subject and caregiver(s) must reside at a location to which study drug can be delivered and have been at their present residence for at least 4 weeks prior to Screening

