Abbreviations: AE=adverse event; EOT=end of treatment; ET=early termination; SAE=serious adverse event

Study visits may be done in the clinic or off-site. Study visits may be done off-site at the discretion of the Principal Investigator and only with the prior approval of the Sponsor or Medical Monitor. The EOT visit should be done in the clinic whenever possible. When a study visit takes place off-site, the physical examination will not be required. Weight should be measured whenever possible at off-site visits.

b Vital signs will include body temperature, resting respiration rate, sitting systolic and diastolic blood pressure, and pulse rate. The sitting blood pressure should be measured after the subject has been sitting or supine for ≥3 minutes.

Pharmacokinetic samples will not be collected at the Week 104 visit or at an ET visit during Treatment Period B. Pharmacokinetic samples will be collected, if possible, at the visit immediately following any SAE or following any AE leading to discontinuation.

- d At the Week 104 EOT/ET visit, the caregiver diary will be returned and reviewed, but no diary will be dispensed.
- ^e Caregiver interviews will be conducted remotely via telephone during Treatment Period B, at or before the final study visit (Week 104 [EOT/ET]). Participation in the caregiver interview is an optional component of the study requiring a separate informed consent.
- f Study drug will be dispensed at the site during the Baseline visit when the visit is conducted in the clinic. For the remainder of the study, investigational product will be shipped directly to the subject. Study drug shipment, return, and accountability will be performed in accordance with the drug distribution plan.
- A 30(+4)-day safety follow-up telephone or telemedicine contact is to be completed for subjects who complete the treatment period of the study or discontinue prematurely from the study (and do not begin to take marketed trofinetide within the 30 days after completing the treatment period of the study).

TABLE OF CONTENTS

SPONS	SOR SIGNATURE PAGE	2
DECLA	ARATION OF INVESTIGATOR	4
PROTO	OCOL SYNOPSIS	5
TABLE	OF CONTENTS	20
LIST O	F TABLES	25
	F FIGURES	
	F ABBREVIATIONS AND DEFINITION OF TERMS	
1	INTRODUCTION	
1.1	Background Information	
1.2	Investigational Product	
1.3	Previous Clinical Experience	
1.3.1	Clinical Pharmacology	
1.3.1.1	Linearity and Dose Proportionality	
	Comparison of Single-Dose and Multiple-Dose Pharmacokinetics	
	Absorption	

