1.4.1 Rationale for Study Design

A placebo-controlled study design is not feasible in this population because of the small numbers of patients with Rett syndrome in this restricted age range. It would be necessary to randomize a large number of patients in order to make any conclusions about differences between patients treated with active drug and those treated with placebo. In addition, interpretation of the efficacy data for an interventional treatment during the regression phase of RTT would present a challenge. The pattern and timing of the regression period varies among patients and would be difficult to characterize even in a large controlled study. The design of the Phase 3 Study 003 was deliberate in attempting to reduce the impact of disease variability in the evaluation of efficacy of trofinetide in RTT: an age cut-off of ≥5 years was selected for both the Phase 2 Study 002 and the Phase 3 Study 003 and both studies have an inclusion criterion requiring the patients to be post-regression at Screening.

Because demonstrating efficacy is not the primary focus of this study, the starting dose is relatively low and increases toward the target dose are made each week in a stepwise fashion, taking into account how well the subject tolerates the medication (see Section 1.4.2). PK data

Final Version: 1.0

Final Version: 1.0 Clinical Study Protocol Amendment 2 Date: 19 December 2022

collected during treatment will provide information on the exposure to drug achieved by the doses the subjects reach, and can later be compared to the exposures associated with benefit in the other studies of trofinetide in RTT. Data from 10 patients is sufficient to provide the PK and tolerability data that may be compared to the data from studies of older patients with RTT.

Period A is 12 weeks long to mirror the 12-week length of Study 003. Period B mirrors the open-label studies, Study 004 and Study 005.

Like Study 005, Period B is designed to give subjects in the study the ability to receive open-label treatment with trofinetide until it becomes commercially available in the US, or until development of trofinetide for RTT is discontinued.

It is estimated that the length of the study will provide enough time on treatment from the time the first subject enters the study until trofinetide is available, or until it becomes apparent that trofinetide will not be marketed in the US.

1.4.2 **Rationale for Dose Selection**

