7.3 Time Period and Frequency for Event Assessment and Follow-up

Adverse events will be recorded from the time informed consent is obtained through the study safety follow-up period. If an AE is ongoing at the end of the study safety follow-up period, every reasonable attempt should be made to follow and appropriately treat the subject until the AE resolves or until the Investigator deems the AE to be chronic or stable.

In the event that a subject discontinues and has an ongoing AE at the time of discontinuation (Section 4.4.2) or is withdrawn from the study because of an AE, a blood sample should be collected and the subject should be followed and appropriately treated until the AE resolves or until the Investigator deems the AE to be chronic or stable.

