7.4.2 Serious Adverse Event Reporting

The reporting of SAEs by the Sponsor or designee to the regulatory authorities is a regulatory requirement. Each regulatory authority has established a timetable for reporting SAEs based upon established criteria.

Serious AEs must be reported within 24 hours of discovery to the Sponsor or its designee; use the appropriate form for initial and/or follow-up reporting.

In the event an SAE or an AE leading to withdrawal is reported, a blood sample for determination of whole blood concentrations of trofinetide will be collected.

At a minimum, events identified by the Sponsor to require expedited reporting as serious, unexpected, and related to study drug must be brought to the attention of the responsible institutional review board/ethics committee (IRB/EC), as per applicable regulations. These will be provided by the Sponsor after their assessment. For European Union member states, the Sponsor or its designee will provide reports of suspected unexpected serious adverse reactions (SUSARs) directly to the ECs, as required by local legislation. In all other countries, it is the Investigator's responsibility to provide these expedited reports to the responsible IRB/EC. It is also the Investigator's responsibility to notify the responsible IRB/EC regarding any new and significant safety information.

Study: ACP-2566-009 Clinical Study Protocol Amendment 2

When an SAE occurs, Investigators will review all documentation related to the event and will complete the paper SAE form with all required information (for initial and/or follow-up information) and fax or email (within 24 hours of discovery) to the contact information provided on the SAE form.

Subjects will be followed through the safety follow-up period (i.e., 30[+4] days after last dose of study drug) for any SAEs and/or other reportable information until such events have resolved or the Investigator deems them to be chronic or stable.

In the event of any SAE (other than death), the study subject's caregiver will be instructed to contact the Investigator (or designee) using the telephone number provided in the ICF. All subjects experiencing an SAE will be seen by the Investigator or designee as soon as is feasible following the report of the SAE.

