7. SUBJECT DISPOSITION

The number and percentage of subjects who completed the study or discontinued early and the reason for study discontinuation will be summarized using the Safety Analysis Set.

The number of caregivers who consented and participated in the optional exit interview, and the number of subjects who took commercially marketed trofinetide within 30 days after study completion will also be summarized using the Safety Analysis Set.

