15.2 Adverse Events

Adverse events will be coded using MedDRA dictionary version 24.0.

An AE (classified by preferred term) will be considered a treatment-emergent AE (TEAE) if started after first dose administration and no later than last dose date + 30 days.

The event counts, the number, and percentage of subjects reporting TEAEs will be tabulated by system organ class (SOC) and PT; and by SOC, PT, and maximum severity. A subject is counted at most once per SOC and PT even if the subject has more than one TEAE. A subject is counted at most once per SOC and PT at the maximum severity for the summary by maximum severity. The display in these tables will be sorted alphabetically by SOC and then by descending subject frequency for the PTs within each SOC.

The event counts, the number and percentage of subjects with any TEAEs will also be tabulated by PT without SOCs. This table will be sorted by descending subject frequency.

Treatment-emergent SAEs, TEAEs leading to study drug withdrawn, and TEAEs related to study drug will be summarized by SOC and PT. The tables will be sorted alphabetically by SOC and then by descending subject frequency for the PTs within each SOC. In addition, the incidence of fatal treatment-emergent AEs (i.e., events that cause death) will be summarized separately by SOC and PT.

An AE listing by subject will display all events, including those which are not treatment-emergent, and will include the verbatim term in addition to the MedDRA SOC and PT. This listing will also include all relevant eCRF data associated with the event: date of onset, date

resolved, date of last dose, severity, frequency, outcome, relationship to study drug, and action taken with study drug. Separate listings will be presented for treatment-emergent SAEs, TEAEs leading to study drug withdrawn, fatal TEAEs (if any), and TEAEs related to COVID-19 infection.

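### The 30-day safety contact is waived for girls who start marketed trofinetide, but Protocol 7.4.2 and the SAP's TEAE window make no matching exception

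*Protocol*

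**What the plan says.** Protocol 3.1.4 owes the follow-up contact to girls who complete treatment or discontinue early "and do not begin to take marketed trofinetide within the 30 days after completing the treatment period of the study". The same condition stands in the synopsis, in footnote g of Table S-2 and in footnote g of SAP 21.2. On content, 3.1.4 says: "The telephone or telemedicine contact includes assessment of concomitant medications and treatments and assessment of AEs".

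The AE sections carry no such condition. Protocol 7.3: "Adverse events will be recorded from the time informed consent is obtained through the study safety follow-up period". Protocol 7.4.2: "Subjects will be followed through the safety follow-up period (i.e., 30[+4] days after last dose of study drug) for any SAEs".

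In the SAP, Section 15.2 treats an event as treatment-emergent if it "started after first dose administration and no later than last dose date + 30 days". Marketed trofinetide is not mentioned there. It appears in Section 7, which tabulates "the number of subjects who took commercially marketed trofinetide within 30 days after study completion".

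Protocol 1.4.1 explains why switching is foreseen: Period B gives girls "the ability to receive open-label treatment with trofinetide until it becomes commercially available in the US", or until development stops.

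**The concern.** TEAEs are a primary endpoint, and the end of the TEAE window is the part of the study that the waived contact was meant to cover. If a girl switches within 30 days, two things happen under the plan as written.

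- Between her end-of-treatment or early-termination visit and her first marketed dose, nobody is scheduled to ask about new AEs.
- From her first marketed dose to day 30, an event that happens to be reported is counted against study drug, although she is then taking the commercial product.

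The first can lower the TEAE count and the second can raise it, and the planned tables would show neither. The contact is also where post-treatment medication would be asked about. It is therefore waived for exactly the girls whose marketed-drug start SAP 7 wants to count.

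**Working it through.** The plan states no figure to reproduce: the study is descriptive, and its sample size is not statistically based (Protocol 9.2, 9.3). The check compares the sections, followed by a scale calculation.

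**Sections side by side**

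| Place | Who or what it covers | Exception for marketed drug |
|---|---|---|
| Protocol 3.1.4, synopsis, Table S-2 fn g, SAP 21.2 fn g | 30(+4)-day contact | Yes, contact waived |
| Protocol 7.3 | AE recording to end of safety follow-up | None |
| Protocol 7.4.2 | SAE follow-up to 30(+4) days after last dose | None |
| SAP 15.2 | TEAE window to last dose + 30 days | None |
| SAP 7 | Count of girls who started marketed drug | Count only |

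**What remains after end of treatment.** In Table S-2 the contact is the only AE assessment after Week 104/ET. The caregiver diary is returned at that visit and no new one is given (footnote d). Protocol 7.4.2 keeps SAE reporting within 24 hours of discovery and tells caregivers to contact the investigator about SAEs. Protocol 4.4.2 and 7.3 keep follow-up of AEs that are ongoing or led to discontinuation. The category left without a scheduled route is new, non-serious AEs with onset after the final visit. Section 1.5.1 names diarrhea and vomiting as the most notable tolerability issue and says most diarrhea cases in Study 002 were mild or moderate, so this category matters here.

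**Days per girl.** Let d be the days from last study dose to first marketed dose, with the final visit taken to fall on the day of the last dose. The 30-day window splits into d days off drug, unasked, and 30 - d days on marketed drug, attributed to study drug if an event is reported.

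| d | Off drug, unasked | On marketed drug, inside TEAE window |
|---|---|---|
| 1 | 1 | 29 |
| 15 | 15 | 15 |
| 29 | 29 | 1 |

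**Number of girls.** The documents give no switching share, so it is an assumption. Girls without the contact = share x N, with N = 10 to 15 (Protocol 9.3):

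- 0%: 0
- 25%: 0.25 x 10 = 2.5 to 0.25 x 15 = 3.75
- 50%: 5 to 7.5
- 100%: 10 to 15

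Window person-days without the scheduled contact = 30 x number of switchers. This runs from 0 to 300 of 300 for N = 10, and from 0 to 450 of 450 for N = 15.

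**Share of the whole TEAE period.** 104 weeks x 7 = 728 days; 30 / (728 + 30) = 4.0% for a girl who completes.

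**Chance that it matters at all.** If each of k switchers has probability p of some event in the window, P(at least one) = 1 - (1 - p)^k. The documents give no p; 5%, 10% and 20% are assumed.

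| k | p = 5% | p = 10% | p = 20% |
|---|---|---|---|
| 5 | 23% | 41% | 67% |
| 10 | 40% | 65% | 89% |
| 15 | 54% | 79% | 96% |

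**The case against.** The waiver looks deliberate. It is repeated consistently, and SAP version 2.0 added the matching count of switchers. A girl who switches stays on the same active substance. Study drug clears fast: Protocol 1.3.1.6 gives a terminal half-life of about 13 hours, so five half-lives are 5 x 13 = 65 hours, under three days. Most of the 30-day window is therefore beyond study-drug exposure, and a girl who switches straight after her final visit, where AEs are assessed, has almost no off-drug time to lose. The AE listing shows onset date and last dose date, and SAP 12 tabulates and lists post-treatment medications, which would include marketed trofinetide.

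Much of this stands, and it limits the size of the point. It does not remove the mismatch. If time on marketed drug is not study time, SAP 15.2 should separate it; at present it does not. The half-life argument applies equally to girls who do not switch, for whom the full window is kept. The listings help only if the marketed-drug start date is captured, and the scheduled occasion for asking about it is the waived contact. Sites may learn of a switch in other ways, for example when they already provide the girl's care, but the documents specify none.

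A reader might infer that switchers have no safety follow-up. They do: SAE reporting and follow-up of ongoing AEs continue. A reader might also infer that the SAP treats the unasked days as observed and event-free time. It plans event counts and subject percentages with no person-time denominator, so last dose + 30 days is a limit for classifying reported events and makes no statement about follow-up.

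**Conclusion.** The inconsistency is real and worth correcting. Its effect is bounded. For girls who begin marketed trofinetide within 30 days, new non-serious AEs before the switch have no scheduled ascertainment, and reported events after the first marketed dose are tabulated as study-drug TEAEs up to last dose + 30 days.

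The number affected could be anything from none to all of 10-15 subjects. The loss per girl is her own gap between products, at most 30 days. The window is about 4% of a completer's TEAE period, but it is the whole of the post-treatment part.

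Three stronger statements are not supported.

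- That the window will be empty for many completers: Protocol 1.4.1 makes switching the foreseeable exit, but no rate or timing is given.
- That 7.4.2 expressly covers every subject: it says subjects, with no exception stated, which makes this a conflict of wording to reconcile.
- That the waiver certainly reaches early discontinuers: its clock starts at completion of the treatment period, which they do not reach, so its application to them is ambiguous.

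**What to change.** 1. In Protocol 3.1.4, the synopsis, Table S-2 footnote g and SAP 21.2 footnote g, drop the condition on marketed trofinetide so that the existing 30(+4)-day telephone or telemedicine contact applies to every subject. This brings them into line with 7.3 and 7.4.2, settles the position of early discontinuers, and needs no advance knowledge of a switch.
2. Record the date of the first marketed dose at that contact. SAP 7 then has a defined source for its count.
3. In SAP 15.2, keep last dose + 30 days as the outer limit. Flag TEAEs with onset on or after the first marketed dose and tabulate them separately. Cutting the window at the first marketed dose is less good, because it would remove from the tables any study-drug event that appears after the switch.
4. Report how many subjects had the post-treatment window observed.

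The cost is one call per switching girl, a few more AEs to record, and one extra split in the TEAE tables.
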